5.6 Sample Size Determination

Although the SF-MPQ data is the basis of our specific aim, we do not have our own preliminary SF-MPQ data. So we will base our sample size on our most robust data, that being nerve block duration from our observational data (40 hr mean, with 14 hr standard deviation). Hip replacement and knee replacement surgery are different procedures requiring anatomically different nerve blocks as described above, so we will consider these samples as separate. We consider a doubling of the nerve block duration (15 hr for plain bupivacaine, 30 hr for bupivacaine-CBD) as a clinically significant difference with respect to the military objectives of evacuation and transport. We forecast that as a single-drug (and based on historical literature), the standard deviation of plain bupivacaine duration would be half of the 15 hr projected duration (i.e., 7.5 hr). Due to likely variability in study participant responsiveness to the 4-drug mixture, we predict that the standard deviation of the bupivacaine-CBD treatment would also be half of the projected 30 hr duration (i.e., 15 hr). We believe that the 30 (SD=15) hr duration for bupivacaine-CBD is a reasonably conservative duration based on our preliminary data of 40 (14) hr block duration. Using a 2-tailed t-test with $\alpha=0.05$, 20 patients per procedure for bupivacaine treatment, and 80 patients per bupivacaine-CBD treatment would yield 95% statistical power. This sample size will also accommodate for our multiple secondary aims. Attrition of 6 active control treatment patients ($n=14$) and of 24 MMPNA-treated patients ($n=56$) will still yield just over 80% statistical power. All calculations were performed using IBM SPSS SamplePower version 3.0.1, Chicago, IL.

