4.4 Data Collection

Primary Outcome – Pain

Pain - Pain will be measured by the Short-Form McGill Pain Questionnaire (36). (SF-MPQ, version 2) and the Defense and Veterans Pain Rating Scale (DVPRS, which entails a 0-10 numeric rating scale along with step-function visual cues, color-coded visual cues, and verbal descriptors of pain intensity). The specific aim is the 24-hour pain severity as measured by the SF-MPQ. The DVPRS will be used to assess (i) “rebound pain” for pain with movement, compared with baseline, during and after nerve block analgesic effects are experienced and (ii) “block duration” (11) for time interval between block placement and peak postoperative DVPRS score with movement.

Exploratory Outcomes – Physical Function, Other Symptoms, and Recovery from Anesthesia

Data will be recorded by the research coordinator and/or VAPHS Staff Physical Therapists and/or “without compensation” (WOC) physical therapists hired through the University of Pittsburgh specifically for the care of study patients.

Data Management System

Data management will be coordinated at VAPHS by StatCore. Data entry will be primarily performed using the VA’s REDCap software (https://vhacdweb05.vha.med.va.gov/redcap_v6.0.27/index.php?pid=1440) via laptop or desktop personal computers. Data will never reside on the data collection devices, which serve only as portals to the password protected database. Only authorized members of the study team will have access. Data will reside on the VA Informatics & Computing Infrastructure (VINCI) server – which is also password protected and independent from all other servers. Data will be downloaded from the REDCap server by StatCore for analytic and data management purposes. Downloaded data will reside on a password-protected VAPHS secure shared drive. REDCap is a secure web-based platform that can only be accessed through the VA intranet, and it is situated behind the VA firewall. Account login information is required, and then the data are stored on the REDCap server. The data to be entered (and catalogued in a detailed data dictionary) are password-protected within REDCap via login requirements, and the downloaded data are secured by permission only access to the shared drive (\\\whapthshare\Nerve_Block_Study\).

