5.0 Statistical Analysis

5.1 Analysis Plan

Data will first be assessed for outliers (+/- 2 SD from the mean) and normality. Outliers will be corrected, if possible, or dropped from the analyses. Distribution, measures of central tendency, variability, and normality will be examined. Data transformations or non-parametric techniques will be applied as needed. We will delete observations with missing values. Spearman correlation coefficients will be computed to examine associations between nerve block drug treatments, replacement surgery

type (hip versus knee), and the outcome measures (SF-MPQ, SF-8, SF- 36, WOMAC, FIM, repeated chair stand test, Opioid Symptom Distress Scale, Defense and Veterans Pain Rating Scale and its Supplemental Questions) from all time points (1 day, 2 day, 3 day, 4 day, Follow-Up Visit 1, Follow-Up Visit 2). Associations between the outcomes across time points will also be examined with Pearson (SF-MPQ, SF-8, SF-36, WOMAC, repeated chair stand test, Opioid Symptom Distress Scale) and Spearman (FIM, Defense and Veterans Pain Rating Scale and its Supplemental Questions) correlation coefficients. We will test all hypotheses and aims by conducting longitudinal multi-level modeling. The level-one unit will be the repeated measures across time, the level-two unit will be the individual patient, and the level-three unit will be nerve block type and surgical site (knee versus hip) groupings (with additional analyses involving age and diabetes status, reflecting the randomization strata). This mixed model procedure will allow the assessment of outcome and exposure variables relationships while adjusting for covariates, and separate assessments of fixed and random effects (i.e., group and individual-level data) using highly correlated repeated measures data. Covariates included in modeling will be age, diabetes status, gender, weight, smoking status, initial health status (e.g., baseline SF-8 / SF-36 and WOMAC), and concurrent general health status (e.g., daily SF-8, subsequent SF-36, and WOMAC).

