The **primary hypothesis** of an improvement in pain (measured by the SF-MPQ- version 2) 24 hr after surgery during in-hospital recovery comparing plain local anesthetics versus ISOC MMPNA will be tested using a mixed model. This procedure will test for nerve block drug treatment and surgical site (hip versus knee) effects, as well as an interaction between them. Differences in pain levels will also be examined across the study's day-of surgery, 1, 2, 3, and 4 day, and Follow-Up Visit 1 and Follow-Up Visit 2 time points. The secondary aims of short- and long-term physical therapy and rehabilitation-related benefits will also be examined for nerve block drug treatment and surgical site by a mixed model. The tertiary aim to determine differences in opioid-related side effects will use a mixed model. As with other analyses, there will be an examination for nerve block drug treatment and surgical site effects, as well as an interaction between them, along with analyses of the other randomization strata (age, diabetes) as described above.

The **exploratory aims** of physical therapy progress, return-to-home benefits, etc. will be examined using a mixed model. This procedure will test for nerve block type and surgical site effects, as well as an interaction between them. Number of days from the joint replacement procedure to the patient's home discharge will be assessed. Pain responses, as measured by the SF-MPQ – version 2, and use of postoperative opioids with additional measurement by the Opioid-Related Symptom Distress Scale will also be assessed. General health status will be evaluated with the SF-8 and SF-36. Measures of pain, analgesic side-effects, and general health status will be covariates included in the modeling of the effect of MMPNA on return-to-home.

Only after all data are analyzed and results are checked and verified by the biostatisticians will the study be unblinded.

5.2 Adverse Events. For adverse events, we will calculate cumulative probability using survival analysis techniques such as the product-limit estimator. Unlike proportions, product-limit estimators can be applied at various times following randomization, and can take into account when adverse events occur. The six-week incidence (and 95% CI) of individual adverse events by organ system and relatedness to the study will be calculated for each group. We will estimate the incidence of adverse

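### The block-duration powers stated in section 5.6 do not follow from its printed inputs, which give higher values; the error is conservative and leaves the sample size unchanged

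*Combined protocol and SAP*

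**What the plan says.** Section 5.6 acknowledges that the sizing outcome is a substitute: "Although the SF-MPQ data is the basis of our specific aim, we do not have our own preliminary SF-MPQ data". It uses block duration instead and takes knee and hip replacement one at a time ("so we will consider these samples as separate"). The printed inputs are means of 15 h for plain bupivacaine and 30 h for the four-drug block, SDs of 7.5 h and 15 h, a two-tailed t-test and alpha 0.05. For 20 controls per procedure it states that "80 patients per bupivacaine-CBD treatment would yield 95% statistical power". After losing 6 controls and 24 four-drug patients (14 vs 56), the design "will still yield just over 80% statistical power".

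The primary outcome is different. Section 4.4 says: "The specific aim is the 24-hour pain severity as measured by the SF-MPQ". Under section 5.1 the primary hypothesis, "comparing plain local anesthetics versus ISOC MMPNA will be tested using a mixed model", and of that model it says: "This procedure will test for nerve block drug treatment and surgical site (hip versus knee) effects, as well as an interaction between them". Section 5.4 projects interim looks for each procedure separately, leaves the monitoring method to be agreed with the data and safety monitoring board, and gives that board the decision on termination if the specific aims have been met.

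**The concern.** Every input needed for the two duration powers is printed, so a reader can recompute them, and the results disagree with the text. The gap at 14 vs 56 is at least 11 percentage points, too large for rounding. Either the calculation used inputs other than those printed, or the figures were transcribed wrongly. The record of how the trial was sized is therefore unreliable as written, even though the direction is harmless.

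Two related gaps make the text harder to use. These are the only powers in the plan and they belong to duration; no SD, target difference, power or detectable difference is given for the 24 h SF-MPQ-2. Sizing and interim looks are per procedure, while the primary hypothesis is tested in one model covering both. Such a model can yield a combined or a per-procedure effect, and the plan does not say outright which one carries the final conclusion.

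**Working it through.** **Inputs (section 5.6).** Difference 30 − 15 = 15 h; SDs 7.5 h (control) and 15 h (four-drug); two-sided alpha 0.05; 20 vs 80, and 14 vs 56 after attrition.

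**Formula.** SE = SD × √(1/n₁ + 1/n₂); noncentrality = 15/SE; power is the probability that a noncentral t with n₁ + n₂ − 2 degrees of freedom exceeds the critical value. The square-root factor is 0.250 for 20 vs 80 and 0.299 for 14 vs 56. The critical values are 1.984 (98 df) and 1.995 (68 df).

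**Attempt to reproduce 95% and just over 80%.** The result depends on how the two SDs are combined:

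| Variance convention | 20 vs 80 | 14 vs 56 |
|---|---|---|
| SD 15 h in both arms | SE 3.75, noncentrality 4.00, power 97.7% | SE 4.48, noncentrality 3.35, power 91.0% |
| SD pooled by sample size (13.87; 13.88) | SE 3.47, noncentrality 4.33, power 99.0% | SE 4.15, noncentrality 3.62, power 94.6% |
| Root-mean-square SD (11.86) | SE 2.96, noncentrality 5.06, power 99.9% | SE 3.54, noncentrality 4.23, power 98.7% |
| Welch (df 61.3; 42.1) | SE 2.37, power >99.9% | SE 2.83, power 99.9% |
| Ordinary pooled t-test, simulated with SDs 7.5 and 15 h | about 99.96% | about 98.9% |

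Even the least favourable row exceeds the stated figures by 2.7 points (97.7 − 95) and about 11 points (91.0 − 80).

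The simulated row exceeds the sample-size-pooled row because the larger arm has the larger SD. The true SE of the difference is √(7.5²/20 + 15²/80) = √(2.81 + 2.81) = 2.37 h, against the 3.47 h that the equal-variance formula assumes.

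**Where the stated pair might come from.** Two settings come close: alpha 0.01 with the SD pooled by sample size (95.3% and 82.9%), or alpha 0.05 with SD √(7.5² + 15²) = 16.77 h (94.3% and 83.9%). Neither is what the text prints, and the documents do not let one choose between them. With a single common SD at alpha 0.05, 95% would need about 16.5 h and 80% about 17.7 h. Those two values differ from each other, and both exceed either stated SD.

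**Primary outcome.** With no SF-MPQ-2 SD in the documents, only SD units are possible. The detectable difference at 80% power (unadjusted t-test, two-sided 0.05, before any interim adjustment) is:
- per procedure, 20 vs 80: 0.71 SD
- combined, 40 vs 160: 0.50 SD

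For comparison, the duration assumption is 15/13.87 = 1.08 pooled SD. High power for duration therefore does not carry over to a smaller standardised effect on pain.

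**The case against.** The strongest reply is that nothing depends on this. The stated powers are too low, so the trial is not too small for duration, and no patient number changes. That stands, and it limits the point to a correction of the text.

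Second, a reader might take 99.0% and 94.6% as the correct replacements. That is too firm. Those values put one pooled SD into an equal-variance formula although the stated SDs differ; for 14 vs 56 the result is about 4 points below the rejection rate of the test itself (98.9%). The replacement must come with its formula.

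Third, the use of duration is disclosed and the powers are presented as duration powers. A reader might infer that the plan claims 95% power for pain; it does not. The SD-unit figures also only restate the sample sizes, and without an SD or an important difference they cannot show whether the trial is adequate. Adding them is useful but optional.

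Fourth, sections 1.0 and 5.1 describe one specific aim tested in one model, which reads most naturally as a combined treatment effect plus an interaction; separate sizing is compatible with that. A reader might infer an inflated error rate of 1 − 0.95² = 9.75%. That applies only if two separate final tests are run at 0.05 each, which section 5.1 does not propose. Section 5.4 already settles that the interim looks are per procedure. It does not say whether a result in one procedure can end the study for both.

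Finally, a reader might take the 44 × 5 = 220 assignments in section 4.2, against 200 patients, as evidence that the attrition scenario is pessimistic. Randomization is stratified by procedure, age and diabetes (2 × 2 × 2 = 8 strata), so the surplus may only allow for incomplete blocks. It says nothing about attrition.

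**Conclusion.** The two duration powers in section 5.6 are wrong as written. At the printed alpha the inputs give 97.7% to over 99.9% for 20 vs 80 and 91.0% to 99.9% for 14 vs 56, with about 99.96% and 98.9% for the stated test under the stated SDs. The simulated values assume normally distributed durations. The misstatement is conservative and the sample size is unaffected. A wrong alpha or SD entry is possible but cannot be established from the documents.

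The absence of any precision statement for the 24 h SF-MPQ-2 is a disclosed gap, not an arithmetic error. The 0.71 and 0.50 SD values ignore any gain from the covariates planned in section 5.1 and any alpha spent at interim looks. The unit of the final primary conclusion, and the reach of an interim result in one procedure, need a clarifying sentence. The documents do not show that the error rate is inflated.

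**What to change.** 1. Recheck the stored sample-size run, correct the two powers in section 5.6, and name the alpha, the SD (or SDs) and the formula used.
2. State that these powers apply to block duration only. Optionally add that, because no SF-MPQ-2 SD or target difference is available, the primary 24 h comparison is described in SD units: about 0.71 SD per procedure (20 vs 80) or 0.50 SD combined (40 vs 160) at 80% power, by unadjusted t-test, two-sided 0.05, before interim adjustment.
3. As a secondary clarification across sections 5.1, 5.4 and 5.6, state that the final primary conclusion rests on the combined treatment effect or, if it is per procedure, how alpha is shared between the two. State also whether an interim result in one procedure can stop the whole study.

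The cost is one check of a stored calculation and a few sentences of protocol wording, with no extra patients. If the conclusion is made per procedure, sharing alpha costs some power. A precision statement for pain will also look less favourable than the duration powers do.

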6.0 Subject Population

6.1 General Characteristics

This study will enroll veterans undergoing a total knee or hip replacement, no older than age 85.

6.2 Vulnerable Subjects and Special Populations

Vulnerable subjects will not be enrolled into this research study.

6.3 Incompetent Subjects

Incompetent subjects will not be enrolled into this research study.

6.4 Inclusion/Exclusion Criteria

Inclusion Criteria:

Subjects must meet all of the following inclusion criteria to be eligible for participation in this study.

1. Age between 18 and 85, and undergoing a total knee or hip replacement.
2. Fluent in English, decision competent, willing and able to provide written informed consent, and able to complete the study's schedule of assessments.
3. Able to walk >3m without an assisting device.
4. Have a BMI $\leq 40 \text{ kg/m}^2$.

Exclusion Criteria:

Subjects who meet *any* of the following exclusion criteria will not be enrolled in this study.

1. Current participation in another orthopedic/PT/rehab/anesthesiology interventional clinical trial.
2. Are at significant behavioral risks or have refractory major psychiatric disorders.
3. Revision surgery on the same extremity.
4. Have an ASA Physical Status classification of 4 or higher.
5. Have been diagnosed with clinically significant neuropathy with its origins in either diabetes or other causes; have neuromuscular disease that would influence data collection.
6. Have a surgically-fused lumbar spine, or a spinal cord simulator, or other condition that would contraindicate or prohibit the conduct of spinal anesthesia.
7. At significant risk for postoperative substance abuse, or immediate-postoperative substance abuse withdrawal symptoms (alcohol, cocaine, enrolled in methadone or buprenorphine opioid withdrawal programs, etc.). Previous or current use of marijuana will not be an exclusion for study enrollment.
8. Are undergoing TKA/THA for a tumor.
9. Have contraindications (e.g., anaphylaxis) to any of the study drugs.
10. Have a systemic fungal infection.
11. Have a known hypersensitivity to bupivacaine hydrochloride or to any local anesthetic of the amide-type or to other components of bupivacaine hydrochloride solutions.
12. Have a known or suspected buprenorphine hypersensitivity (not including nausea and/or vomiting).
13. Have a GI obstruction.
14. Have paralytic ileus.
15. Pregnant women
16. Have had a kidney or liver transplant.

Veteran subjects will not be excluded from participation based on smoking status, diagnosis of obstructive sleep apnea, or baseline monitored consumption of therapeutic opioids for documented

medical indications; instead, these variables will be codified and quantified for subsequent covariate statistical analysis. Prior to study enrollment, the principal investigator has the final decision regarding patient eligibility.

Pregnancy is an exclusion criterion for surgery and is checked by the clinical team. The Research team will confirm that the pregnancy test has been done (where applicable).

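### Sleep apnea and baseline opioid use are promised as covariates but missing from the Section 5.1 list, and no pre-operative SF-MPQ-2 score is named as a covariate in the primary 24-hour SF-MPQ-2 model

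*Combined protocol and SAP*

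**What the plan says.** **Eligibility (Section 6.4).** Smoking, obstructive sleep apnea and "baseline monitored consumption of therapeutic opioids" for a documented indication are not grounds for exclusion. Instead, "these variables will be codified and quantified for subsequent covariate statistical analysis".

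**Covariates (Section 5.1).** The list reads "Covariates included in modeling will be age, diabetes status, gender, weight, smoking status, initial health status (e.g., baseline SF-8 / SF-36 and WOMAC"), followed by "concurrent general health status (e.g., daily SF-8, subsequent SF-36, and WOMAC"). Of the three variables promised in Section 6.4, only smoking appears.

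**Primary model (Section 5.1).** A mixed model is used for the 24-hour SF-MPQ-2 comparison, and the plan describes its terms as follows: "This procedure will test for nerve block drug treatment and surgical site (hip versus knee) effects, as well as an interaction between them". No baseline SF-MPQ-2 term is stated. Pain is named as a covariate only for an exploratory outcome, where pain, side effects and "general health status will be covariates included in the modeling of the effect of MMPNA on return-to-home".

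**Collection (Appendix 1, Section 4.3).** SF-MPQ-2 is marked at the baseline visit and again before the procedure on the day of surgery. Concomitant medications and the CIRS comorbidity scale are recorded at baseline. Section 4.3 names smoking and diabetes among the baseline assessments, but neither sleep apnea nor opioid use.

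**The concern.** Section 6.4 offers covariate adjustment as the alternative to excluding these patients. If the model omits two of the three variables, that eligibility decision has no counterpart in the analysis.

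The pre-operative value of the primary outcome is also a natural covariate for that outcome, and the trial already collects it twice. Leaving it out of the primary model can widen the confidence interval for no saving in data collection.

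The control group is small: 20 per procedure, with Section 5.6 treating hip and knee as separate samples. The stratification in Section 4.2 covers procedure, age and diabetes, but not opioid use or sleep apnea, so a chance difference in either would go unadjusted. An incomplete list also leaves room to choose the adjustment set later.

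**Working it through.** **1. Comparing the sections.**

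| Variable | Promised in 6.4 | Named in 5.1 | Where recorded |
|---|---|---|---|
| Smoking | yes | yes | baseline assessments (4.3) |
| Sleep apnea | yes | no | not named; CIRS may hold it |
| Baseline opioid use | yes | no | not named; baseline concomitant medications may hold it |
| Pre-operative SF-MPQ-2 | not mentioned | no | baseline visit and pre-procedure (Appendix 1) |

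The open wording in Section 5.1 (its e.g.) qualifies health status and is illustrated by SF-8, SF-36 and WOMAC. Opioid consumption is not a health-status score, so the open wording does not bring it in.

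**2. The plan's own figure.** Section 5.6 gives no SF-MPQ effect, standard deviation or correlation. Its 95% power is for block duration (15 hr difference; SDs 7.5 and 15 hr; 20 versus 80; two-sided 0.05). The pooled SD is √[(19×7.5² + 79×15²)/98] = 13.87, and a noncentral t calculation then gives 99.0%, not 95%. At 14 versus 56 it gives 94.6%, against a stated figure of just over 80%. The stated figures are conservative for block duration, and nothing below depends on them.

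**3. Upper limit of the gain.** Let ρ be the correlation of the pre-operative with the 24-hour score (assumed). With no other covariates, residual variance is multiplied by 1 − ρ² and the standard error by √(1 − ρ²).

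- ρ = 0.3: variance factor 0.91 (9% less), SE factor 0.954 (about 5% less).
- ρ = 0.5: variance factor 0.75 (25% less), SE factor 0.866 (about 13% less).

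For an effect with 80% unadjusted power at 20 versus 80 (standardized difference 0.71), power becomes about 83% at ρ = 0.3 and about 90% at ρ = 0.5.

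**4. Gain on top of SF-36 and WOMAC.** Let R be the correlation of those scores with the outcome (assumed 0.3 or 0.5) and c their correlation with baseline SF-MPQ-2 (assumed 0.5 or 0.7). The partial correlation is (ρ − Rc)/√[(1 − R²)(1 − c²)], and its square is the extra fraction of variance removed.

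- ρ = 0.3, R = 0.5, c = 0.5: 0.05/0.75 = 0.067, so 0.4%.
- ρ = 0.3, R = 0.3, c = 0.5: 0.15/0.826 = 0.182, so 3.3%.
- ρ = 0.5, R = 0.5, c = 0.7: 0.15/0.618 = 0.243, so 5.9%.
- ρ = 0.5, R = 0.3, c = 0.7: 0.29/0.681 = 0.426, so 18.1%.

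These are the extremes over all eight combinations, so the range is roughly 0.4 to 18%.

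**5. Cost of adding a covariate.** A useless covariate inflates variance by about 1/(N − 4): 1.0% at N = 100 and 0.5% at N = 200. Section 5.1 also deletes observations with missing values. If a fraction m lacks the covariate, variance becomes proportional to (1 − ρ²)/(1 − m), so the gain is gone at m = ρ²: 4% missing at ρ = 0.2, 9% at ρ = 0.3.

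**6. Chance imbalance.** Suppose 20 to 40% of patients use opioids at baseline (assumption) and sampling is binomial. The exact probability that arms of 20 and 80 differ by at least 15 percentage points is 15% (at 20% users) to 24% (at 40% users).

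**The case against.** **Baseline pain is not wholly ignored.** A reader might infer that the plan never adjusts for it. The documents do not support that. SF-36 has a bodily pain scale (Section 4.3), the whole WOMAC is administered, and baseline values of both are listed covariates. Section 5.1 also compares pain across time points that include the day of surgery. Appendix 1 puts pre- and post-procedure assessments under that heading, so the pre-procedure score may enter as a repeated measure. The plan does not say whether it does, and that ambiguity stands as part of the point.

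**There is no bias.** A reader might infer that omitting opioid use distorts the treatment effect. With randomized treatment it does not, and the test's error rate already allows for chance imbalance. What remains is precision and the ability to account for an imbalance that occurs.

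**The gain may be small.** One might turn 9 to 25% into 20 to 67 extra patients on 200 (200/0.91 ≈ 220; 200/0.75 ≈ 267). Those figures ignore SF-36 and WOMAC and rest on an assumed correlation. Section 2.1 also reports about 36 hours of analgesia with the four-drug block, so many of those patients would still have analgesia at 24 hours. That could weaken the link with pre-operative joint pain. This objection stands, and the patient equivalents should not be used.

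**Adjustment is not free.** It uses degrees of freedom, and the deletion rule can cancel the benefit. This stands too, and the fix has to deal with it.

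**Section 6.4 may mean supportive analyses.** It does not name the primary model. But Section 5.1 lists the two variables for no model at all, so the mismatch remains on either reading. The documents give no reason to expect sleep apnea to predict 24-hour pain; its place in the list rests on the plan's own promise.

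**Conclusion.** The point holds as an inconsistency and a missed, low-cost improvement. Sections 6.4 and 5.1 disagree on sleep apnea and baseline opioid use, and the primary SF-MPQ-2 model names no pre-operative value of its own outcome although two are collected.

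The consequence is some lost precision and no adjustment for chance imbalance with 20 controls per procedure; the validity of the randomized comparison is not affected. At an assumed correlation of 0.3 to 0.5, the variance reduction is at most 9 to 25% alone. It is roughly 0.4 to 18% beyond SF-36 and WOMAC under the assumed correlations among the three measures. The documents supply none of these correlations, so no single figure can be defended.

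**What to change.** In Section 5.1:

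1. Name the pre-procedure SF-MPQ-2 score, or the baseline-visit score if it is missing, as a fixed covariate in the primary 24-hour model. State that it is not one of the post-treatment responses, which settles what the day-of-surgery time point contains.
2. Reconcile with Section 6.4 by adding baseline opioid use, defined from the baseline concomitant-medication record, and sleep apnea. State the coding and data source of each; for sleep apnea, confirm first that CIRS or another baseline record holds the diagnosis.
3. Exempt baseline covariates from the deletion rule. A missing value can be filled without reference to treatment or outcome, for example with the overall baseline mean, so that no randomized patient is lost for this reason.

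Fix this wording before anyone sees results by group. The cost is a few degrees of freedom and a small amount of coding of data already recorded, with no new visits or questionnaires.
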